### **10.7.2 Investigational Medicinal Product Destruction**

Used and unused IMPs will be destroyed by the CMO according to LEO Pharma procedures.

### **10.7.3 Treatment Compliance**

At Visits 2, 3 and 4, the subject should be asked if she/he has used the IMP as prescribed. If a subject is found to be non-compliant, the (sub)investigator should remind the subject of the importance of following the instructions given including using the trial products as prescribed. The degree of non-compliance (number of applications missed, or other deviation) and the reason for it must be recorded in the eCRF. Subjects will be provided with a diary for recording of this information.

## **10.8 Provision for Subject Care following Trial Completion**

In order to ensure appropriate treatment of the subjects after they have completed the trial, the subjects will be treated at the investigator's discretion or referred to other physician(s) according to standard practice.

## 10.9 Reporting Product Complaints

Any defects or issues with the IMP must be reported to LEO Pharma K.K. on the trial specific (paper) Complaint Form within 3 days of first knowledge.

Critical complaints (defined as any defect or issue that has or potentially could have a serious impact for the subject [e.g., SAE]) must be reported to LEO Pharma K.K. within 24 hours of first knowledge.

Complaint forms should contain a detailed description of the defect or issue, including whether it led to an AE. (S)AEs which occur due to a defect or issue with the IMPs will be reported by the investigator as described in sections 9.2 and 9.4.

During the investigation of the product complaint, the IMP(s) must be stored at labelled conditions unless otherwise instructed; the trial site will be notified whether the IMP(s) needs to be returned for further investigation or may be destroyed.

LEO Pharma K.K. contact information for reporting product complaints:

[contact]

E-mail address: [contact]

## 10.10 Emergency Unblinding of Individual Subject Treatment

Not applicable as this trial is open-label.

## 11 Statistical Methods

### 11.1 Determination of Sample Size

The sample size is not based on power calculations (section 6.2), but is based on regulatory considerations, as 80 subjects per treatment group is the number that has been used for a similar trial in Japan to compare different topical formulations of the same active ingredient (28).

### 11.2 Definition of Trial Analysis Sets

All subjects enrolled in the trial (i.e. subjects for whom informed consent has been obtained and who have been registered in a clinical trial) will be accounted for in the clinical trial report.

All randomised subjects are included in the full analysis set and will be analysed for efficacy. Exclusions from the full analysis set can be considered in special cases as described in ICH

E9, section 5.2.1., Full Analysis Set. Any exclusion of subjects from the full analysis set will be justified.

A per protocol analysis set will be defined by excluding subjects from the full analysis set who had less than 75% compliance or based on a review of protocol deviations with justification.

A safety analysis set will be defined by excluding randomised subjects who either received no treatment with IMP and/or for whom no post-baseline safety evaluations are available.

The decisions regarding inclusion/exclusion of subjects and/or subject data from the trial analysis sets will be documented in the analysis set definition document.

## **11.3 Statistical Analysis**

### **11.3.1 Disposition of Subjects**

The reasons for leaving the trial will be presented for all randomised subjects by last visit attended and by treatment group.

### **11.3.2 Demographics and other Baseline Characteristics**

Descriptive statistics of demographics and other baseline characteristics will be presented for all randomised subjects and by treatment group.

Demographics include age and sex. Other baseline characteristics include height, weight, BMI, duration of psoriasis, baseline severity of clinical signs, location of target lesion on the body, concurrent diagnoses (including indications for concomitant medication) and concomitant medication.

Presentations of age, sex, and baseline severity of clinical signs by treatment group will also be given by site.

### **11.3.3 Exposure and Treatment Compliance**

Compliance with treatment instructions will be summarised for each treatment group and for all randomised subjects. The percentage of missed applications for each visit interval (visit 1 to 2, visit 2 to 3 and visit 3 to 4) will be calculated as follows: the number of applications of trial medication missed for a particular visit interval will be divided by the total number of days for the visit interval, and then multiplied by 100 to give a percentage.

The percentage of missed applications for the total treatment period will be calculated as follows: the total number of applications of trial medication missed between Visit 1 and the last on-treatment visit will be divided by the total number of days between Visit 1 and the last on-treatment visit, and then multiplied by 100 to give a percentage.

The percentage of missed applications will be allocated to one of the following categories:  $\leq 10\%$ ,  $>10\%$  to  $\leq 25\%$ ,  $>25\%$  to  $\leq 40\%$ ,  $>40\%$  to  $\leq 50\%$ ,  $>50\%$ .

#### **11.3.4 Analysis of Primary Efficacy Endpoint**

The primary endpoint, as defined in section 5, will be analysed for the full analysis set and for the per protocol analysis set. The analysis using the full analysis set will be regarded as primary, while the per protocol analysis set will act as supportive.

Rates of subjects with the event defined by the primary endpoint, ‘overall improvement rate’ for the target lesion at Visit 4 (end of Week 4), will be compared between treatment groups by means of Fisher’s exact test. Estimated rates, odds ratio and its 95% CI will be presented, together with the p-value from Fisher’s exact test. The number and percentage of subjects with the event will be tabulated for each treatment group and also presented for each site by treatment group.

#### **11.3.5 Analysis of Secondary Efficacy Endpoints**

The secondary endpoints, as defined in section 5, will be analysed for the full analysis set and for the per protocol analysis set. The analysis using the full analysis set will be regarded as primary, while the per protocol analysis set will act as supportive.

The number and percentage of subjects with ‘overall improvement rate’ will be tabulated for Visits 2 and 3 (end of Weeks 1 and 2) and by treatment group.

Descriptive statistics for observed values and change from baseline to Visit 4 (end of Week 4) for the total sign score for the target lesion will be summarised as mean, SD, median, minimum and maximum values for each treatment group.

In addition, for the change in the total sign score, the estimated difference between the treatment groups in the mean change (LEO 90100 foam group – Dovobet® ointment group) will be calculated with 95% confidence interval. The treatment difference of the change in the total sign score at Visit 4 will be estimated with an ANOVA with treatment as fixed effect.

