### Follow-up period

Follow up is only required if there is an AE present at the last visit which is of possible or probable relationship to trial medication or is a serious adverse event (SAE). For non-serious AEs of possible or probable relationship to trial medication, the subject will return 14 days after the subject's last visit or when the final outcome has been established, whichever comes first. If the visit is outside this 14-day window, the reason should be recorded in the subject's medical record, but LEO Pharma does not need to be notified. All related and not related SAEs must be followed up until a final outcome has been established, i.e. the follow-up may continue beyond the end of the clinical trial.

Planned date of enrolment of first subject: Q1 2019

Planned date of completion of last subject: Q2 2019

Estimated number of trial sites and country allocation: 20 trial sites in Japan

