## 6.3 Randomisation

Subjects will be randomly assigned to either LEO 90100 foam or Dovobet® ointment in a 1:1 ratio using a randomisation stratified by investigator site.

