### 11.3.10 General Principles

All significance tests will be two-sided using the 5% significance level. All confidence intervals will be presented with 95% degree of confidence.

An observed cases approach will be used for tabulations of data by visit (i.e. involving only those subjects who attended each specific visit).

Categorical data will be summarised using the number and percentage of subjects in each category and treatment group. Continuous data will be summarised using the mean, median, standard deviation (SD), minimum and maximum values. For laboratory data, the geometric mean and coefficient of variation will be included.

‘Baseline’ value is defined as the value from the latest assessment before treatment, i.e. at Visit 1 (Day 1) before randomisation.

Any changes from the statistical analysis planned in this clinical trial protocol will be described and justified in a protocol amendment/the statistical analysis plan and/or in the clinical trial report dependent on the type of deviation.

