6.6.2 Secondary Efficacy Criteria

The secondary endpoints will be analysed as described in the CTP (section 11.3.5).

There are two different descriptions on total sign score in the CTP (Section 5.2):

- The change in the total sign score from Visit 1 to Visit 4; total sign score is defined as the sum of the scores from the 3 clinical signs assessing severity in the target lesion.
- The change in the sum of the scores (total sign score) for the severity of the three clinical signs (thickness, scaliness, redness) from Visit 1 to the sum of the scores at Visit 4 (end of Week 4) for the target lesion

Since these two endpoints are the identical endpoint, both of them will be regarded as "the change in the total sign score for the target lesion from baseline to Visit 4".

Total sign score is treated as missing when the score for at least one of the clinical signs is missing. LOCF will be used to impute any missing values for Visit 4 for the analysis of change in total sign score from baseline to Visit 4 (end of Week 4).

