Appendix I

Tables, Figures and Listings

Tables, Baseline Characteristics and Investigational Product Data (Module 2)

Tables

101 Trial period by Site (date of first subject visit vs. date of last subject visit): Enrolled subjects

102 Subject enrolment and randomisation: Enrolled and randomised subjects

103_A Age by Site: Randomised subjects

103_B Age, height, weight, and BMI at screening visit: Randomised subjects

104 Sex by Site: Randomised subjects

105 Baseline total sign score of target lesion by Site: Randomised subjects

106 Location of target lesion and duration of psoriasis: Randomised subjects

107 Reasons for withdrawal: Randomised subjects

108 Reasons for withdrawal by last visit attended: Randomised subjects

109 Concurrent diagnoses (excluding psoriasis vulgaris) including indications of concomitant medication at screening visit by MedDRA primary SOC: Enrolled subjects

110 Concurrent medications started before screening visit by ATC: Enrolled subjects

111 Concurrent medications started after screening visit by ATC: Enrolled subjects

112 Time (days) from visit 1 to each trial visit: Randomised subjects

113 Compliance with treatment instructions: Randomised subjects

Tables, Efficacy Data (Module 3)

Tables

E1 Subjects with "overall improvement" for the target lesion at Visit 4 (Week 4 – LOCF):
FAS

E1_A Subjects with "overall improvement" for the target lesion at Visit 4 (Week 4 – LOCF)
by Site: FAS

E2 Subjects with "overall improvement" for the target lesion at Visit 4 (Week 4 – LOCF):
PPAS

EI1 First sensitivity analysis of subjects with "overall improvement" for the target lesion at
Visit 4 (Weeks 4): FAS

EI2 Second sensitivity analysis of subjects with "overall improvement" for the target lesion at
Visit 4 (Week 4): FAS

EI3 Third sensitivity analysis of subjects with "overall improvement" for the target lesion at
Visit 4 (Week 4): FAS

EI4 Fourth sensitivity analysis of subjects with "overall improvement" for the target lesion at
Visit 4 (Week 4): FAS

E3 Subjects with "overall improvement" for the target lesion at Visit 2 and 3 (End of Weeks 1
and 2): FAS

E4 Subjects with "overall improvement" for the target lesion at Visit 2 and 3 (End of Weeks 1
and 2): PPAS

E5 The change in the total sign score for the target lesion from baseline to Visit 4 (Week 4 –
LOCF): FAS

E6 The change in the total sign score for the target lesion from baseline to Visit 4 (Week 4 –
LOCF): PPAS

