E9 The change in severity of clinical sign (redness) for the target lesion from baseline to Visit
4 (week 4 – LOCF): FAS

E10 The change in severity of clinical sign (thickness) for the target lesion from baseline to Visit 4 (week 4 – LOCF): FAS

E11 The change in severity of clinical sign (scaliness) for the target lesion from baseline to Visit 4 (week 4 – LOCF): FAS

E12 Subjects with "substantial resolution" of clinical signs for the target lesion by visit: FAS

E13 The general change for the target lesion from baseline to each visit: FAS

E14 Total sign score for the target lesion from baseline to each visit: FAS

E15 Severity of clinical sign (redness) for the target lesion from baseline to each visit: FAS

E16 Severity of clinical sign (thickness) for the target lesion from baseline to each visit: FAS

E17 Severity of clinical sign (scaliness) for the target lesion from baseline to each visit: FAS

E14_A Total sign score for the target lesion from baseline to each visit: PPAS

E15_A Severity of clinical sign (redness) for the target lesion from baseline to each visit: PPAS

E16_A Severity of clinical sign (thickness) for the target lesion from baseline to each visit: PPAS

E17_A Severity of clinical sign (scaliness) for the target lesion from baseline to each visit: PPAS

E18 Subject assessment of use of medication for "time spent for application" relative to previous topical treatment on target lesion at Visit 4 (Week 4): FAS

E19 Subject assessment of use of medication for "ease of application" relative to previous topical treatment on target lesion at Visit 4 (Week 4): FAS

E20 Summary of statistical analyses for the change in clinical signs (total sign, redness, thickness, scaliness): FAS

Tables, Safety Data (Module 4)

Tables

201 Duration and extent of exposure to treatment: Safety Analysis Set

202 Overall summary of AEs: Safety Analysis Set

203 AEs by primary SOC: Safety Analysis Set

204 AEs by primary SOC and preferred term: Safety Analysis Set

205 AEs assessed as mild by primary SOC and preferred term: Safety Analysis Set

206 AEs assessed as moderate by primary SOC and preferred term: Safety Analysis Set

207 AEs assessed as severe by primary SOC and preferred term: Safety Analysis Set

208 AEs assessed as not related by primary SOC and preferred term: Safety Analysis Set

209 AEs assessed as possibly related by primary SOC and preferred term: Safety Analysis Set

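### The treatment-only ANOVA for change in total sign score leaves out baseline score and site; the estimate stays valid but precision is given away

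*Protocol*

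**What the plan says.** Protocol 11.3.5 gives the treatment difference in change in total sign score, foam minus ointment with a 95% confidence interval, and states that it "will be estimated with an ANOVA with treatment as fixed effect". SAP 6.6.2 refers back to that section and adds only missing-data rules (a total is missing if any sign is missing; LOCF at Visit 4). SAP 6.6.3 uses the same model for redness, thickness and scaliness. No adjusted model appears in either document or in the table list; Table E20 is simply "Summary of statistical analyses for the change in clinical signs (total sign, redness, thickness, scaliness): FAS".

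Both omitted variables are already in the plan:

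- **Baseline.** Protocol 11.3.10 says that the baseline value "is defined as the value from the latest assessment before treatment, i.e. at Visit 1 (Day 1) before randomisation".
- **Site.** Protocol 6.3 allocates in a "1:1 ratio using a randomisation stratified by investigator site", and Protocol 6.1 expects "20 trial sites in Japan".
- **Both together.** Protocol 11.3.2 says that "baseline severity of clinical signs by treatment group will also be given by site", and SAP Appendix I lists Table 105, "Baseline total sign score of target lesion by Site: Randomised subjects".

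**The concern.** Tabulating baseline by site shows an imbalance but does not take it out of the estimate. The two omissions act differently.

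- **Baseline.** A change score subtracts the whole baseline value, which is the right correction only when the slope of Week 4 score on baseline is 1. At any other slope, part of the baseline variation stays in the error and widens both the true spread of the estimate and its interval.
- **Site.** If allocation is balanced within sites, stratification has already removed most site variation from the estimate. Leaving site out of the model puts that variation back into the error term, so the interval is wider than the design requires. This does not depend on the slope.

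Among the secondary efficacy endpoints, this is the only continuous comparison and the only one with a planned between-group estimate and interval; the Visit 2 and 3 rates are only tabulated. The sample size was not based on power (Protocol 6.2 and 11.1), so adequate precision cannot be taken for granted.

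**Working it through.** The plan states no SD, effect size or power for this endpoint, so there is no figure of its own to reproduce.

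**Inputs from the documents.** 180 subjects, 90 per arm (Protocol 6.2); 20 sites, so 180/20 = 9 per site on average; each sign at least 2 at entry (Protocol 7.2), so a baseline total of 6 to 12; ointment m-PASI change −64.3%, SD 24.7 (Protocol Appendix 2, Clinical results; a different scale).

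**Assumed.** SDs of the total sign score, slope, site ICC and block size. None is in these documents.

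**1. Baseline: formula.** Within an arm, with slope b,

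Var(change) = residual variance + (1 − b)² × Var(baseline).

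ANCOVA removes the second term, which is zero only at b = 1.

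**2. Baseline: anchored case.** Let Week 4 score = baseline × (1 − p), with p of mean 0.643 and SD 0.247, independent of baseline. The slope is then 1 − 0.643 = 0.357, about 0.36. With baseline mean 8 and SD 1.3:

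- Residual variance = 0.247² × (8² + 1.3²) = 0.0610 × 65.69 = 4.01.
- Var(change) = 0.643² × 1.3² + 4.01 = 0.70 + 4.01 = 4.71.
- Variance ratio = 4.01/4.71 = 0.852; SE ratio = √0.852 = 0.923, a 7.7% cut.
- SE = √(2 × 4.71/90) = 0.323 for the ANOVA and √(2 × 4.01/90) = 0.298 for ANCOVA.
- 95% half-width (t about 1.973) = 0.64 and 0.59 points.

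With baseline mean 7–9 and SD 1.0–1.6, the SE cut is 4–13%, or 0.03–0.08 points of half-width.

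**3. Baseline: dependence on slope** (baseline SD 1.3, residual SD 2.0). At slope 0.5, for example, Var(change) = 4 + 0.25 × 1.69 = 4.42, and √(4/4.42) = 0.951.

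| Slope | 0 | 0.36 | 0.5 | 0.7 | 0.8 | 1 |
|---|---|---|---|---|---|---|
| SE cut | 16% | 7.7% | 4.9% | 1.8% | 0.8% | nil |

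On a wider grid (baseline SD 1.0–1.6, Week 4 SD 1.5–2.5, correlation 0–0.7) the cut runs from 0 to 32%, with the top only at zero correlation.

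**4. Site: simulation.** 2,500 trials per setting; 20 sites, 180 subjects, equal (9 each) or uneven (1–24) sites; blocks of 4; total residual SD 2.0; site as a random intercept. Ratios of interval width:

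| ICC | Baseline + site vs baseline only | Both vs ANOVA, slope 0.36 | Both vs ANOVA, slope 1 |
|---|---|---|---|
| 0 | 0.994–0.995 | 0.926–0.928 | 0.997–0.998 |
| 0.05 | 0.976–0.977 | 0.911 | 0.979–0.980 |
| 0.10 | 0.952–0.955 | 0.887–0.890 | 0.956–0.957 |

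The small narrowing at ICC 0 comes from chance site-variance estimates and is not a real gain. The true SD of the estimate with and without site differs by at most 0.002. Coverage was 94.9–97.4% for the ANOVA and 94.0–95.5% with both terms. Site as an unpooled fixed effect at ICC 0 widens the interval by 0.7% (equal sites) to 1.3% (uneven sites).

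**5. Separate check of validity and independence of the two losses.** 4,000 runs per setting, 20 sites of 9, true difference −0.5, baseline SD 1.5, Week 4 SD 2.0, site as a fixed effect. Mean half-width under site-stratified blocks of 4:

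| Slope, ICC | ANOVA | + baseline | + site | + both |
|---|---|---|---|---|
| 0.25, 0 | 0.665 | 0.579 | 0.669 | 0.583 |
| 0.25, 0.2 | 0.663 | 0.577 | 0.617 | 0.522 |
| 1, 0 | 0.389 | 0.390 | 0.391 | 0.392 |
| 1, 0.2 | 0.387 | 0.388 | 0.350 | 0.351 |

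Across these and the matching unstratified settings, the mean ANOVA estimate was −0.493 to −0.503. ANOVA coverage was 94.5–95.7% when sites did not differ or allocation was unstratified, and 96.5–97.6% with stratified blocks at ICC 0.2. The planned interval is therefore conservative when sites differ.

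**The case against.** The planned analysis is not an error. It is unbiased, its interval is valid, the primary test does not use it, and no margin or success rule rests on it. The anchored gain is at most 0.08 points of half-width, when each sign is scored in steps of 0.5, and both gains may be zero. The ANOVA difference also equals the difference of the tabulated raw means and matches the unadjusted primary test. All of this is true, and it keeps the point one of precision. The half-point step is a weak comparator, though, because it describes one subject's recording and the interval concerns a mean over 90 per arm.

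Three further objections stand as qualifications:

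- **The site gain is not a better estimator under blocking.** The true spread hardly moves; only the reported interval shrinks.
- **Blocking is an assumption.** The documents give site stratification and sealed envelopes and leave the details to a separate document. Blocks of 2 or 6 at ICC 0.10 give width ratios of 0.953–0.957. Without blocking the ratio is 0.974, and the true SD of the estimate falls from 0.297 to 0.289. A gain remains, but a smaller one in the interval.
- **The remedy needs detail.** A random intercept needs a stated degrees-of-freedom method, although moving from 158 to 177 changes the t quantile by only 0.08%. The lowest coverage of 94.0% is 1.0 point under nominal, where one Monte Carlo standard error is √(0.95 × 0.05/2,500) = 0.44 points; it is the lowest of several settings.

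A supportive baseline-only ANCOVA would capture most of the gain at the anchored slope, but it would leave the less precise interval as the headline and omit the stratification factor.

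**Conclusion.** The concern holds. The treatment-only ANOVA is valid but gives away precision in two separate ways: from baseline unless the slope is near 1, and from site, as an over-wide interval, only if sites differ in change given baseline. At the borrowed slope of 0.36 the baseline loss is 4–13% of the SE. The site loss is about 2.4% of interval width at ICC 0.05 and 4.5–4.8% at ICC 0.10 with blocks.

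The direction is sure; the size is not. It rests on an m-PASI percentage change carried to another scale and on assumed SDs, ICC and blocking. A slope well below 1 is plausible, because baseline totals are 6–12 while substantial resolution means a total of at most 1, but that is inference. For single signs, an illustration on scores of 2–4 in half points gives slopes of 0.36–0.39 and SE cuts of 5–13%. The statement that the estimate is unbiased covers the omission of covariates only, not LOCF or open-label assessment. The change is worth making, but nothing in the trial fails without it.

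**What to change.** Before any treatment comparison is seen, specify as the main estimate and 95% interval in Tables E5, E6 and E20:

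change in total sign score = treatment + baseline total sign score + site,

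with site as a random intercept (REML, degrees-of-freedom method named), or as a fixed effect with a stated rule for pooling small sites. If the site variance is estimated as zero, the random-intercept model reduces to baseline-only ANCOVA. Keep the treatment-only ANOVA as supportive. Use the same form, with each sign's own baseline, in Tables E9–E11 for consistency.

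No new data are needed. Because the protocol names the model, Protocol 11.3.10 requires the change to be described and justified in an amendment or the SAP. Timing is the main constraint: the trial is open-label, Protocol Appendix 5D gives sponsor personnel immediate access to eCRF data, and the SAP is dated 21 June 2019 with approval signatures up to 4 July 2019. The change should be dated and locked under the Blinding Plan cited in SAP section 5. If the slope proves near 1 and sites do not differ, nothing is gained; unpooled fixed site effects would then cost about 1% in width.
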